6.3 Nivolumab with Ipilimumab

Patients who experience PD on single-agent nivolumab, or patients who have experienced allograft loss, may shift to a combination therapy with nivolumab and ipilimumab. During the initial induction period, nivolumab will be dosed at 3 mg/kg and ipilimumab will be dosed at 1 mg/kg. Each will be given by IV infusion over approximately 30 minutes once every 3 weeks for 4 cycles (12 weeks). After the 4th and final induction dose, there will be a six-week gap before beginning maintenance nivolumab therapy. This gap includes the 3 weeks in Cycle 4, thus Cycle 5 (the first cycle of the maintenance period) should begin 3 weeks after the end of Cycle 4. During the maintenance period, nivolumab will be dosed at 480 mg by IV infusion over approximately 30 minutes once every 4 weeks. This maintenance regimen may be continued for up to 21 cycles (84 weeks) regardless of the duration of nivolumab administration prior to transitioning to combination therapy.

Tacrolimus and prednisone administration will continue as described in Section 6.1. Patients who have experienced allograft loss should discontinue tacrolimus regardless of treatment option chosen. Prednisone may be prescribed as needed.

Dosing calculations should be based on the actual body weight. If the patient's weight differs by >10% from the weight used to calculate the original dose, the dose may be recalculated. All doses should be rounded to the nearest milligram. There will be no other dose modifications allowed.

Toxicity management for the combined agents follows the same template guidelines and algorithms that are provided in Section 7 and Appendix B for single agent nivolumab.

When both nivolumab and ipilimumab are to be administered on the same day, separate infusion bags and filters must be used for each infusion, there should be a 30-minute rest period between infusions, and nivolumab is to be administered first. Nivolumab is to be infused over approximately 30 minutes, promptly followed by a saline flush to clear the line of nivolumab and a 30-minute rest period before starting the ipilimumab infusion. Ipilimumab is to be infused over approximately 30 minutes, also followed by a saline flush.

Nivolumab/Ipilimumab Regimen Description					
Agent	Premedications and Precautions	Dose	Route	Schedule	Cycle Length
Nivolumab (Induction)	None, except in the case of an infusion reaction (see Section 6.9)	3 mg/kg	IV infusion over ~30 minutes	Day 1, Week 1 for 4 cycles (Four total doses)	3 weeks
Ipilimumab (Induction)	None, except in the case of an infusion reaction (see Section 6.9)	1 mg/kg	IV infusion over ~30 minutes	Day 1, Week 1 for 4 cycles (Four total doses)	
Nivolumab (Maintenance)	None, except in the case of an infusion reaction (see Section 6.9)	480 mg	IV infusion over ~30 minutes	Day 1, Week 1, starting six weeks after the last dose of ipilimumab	4 weeks
Tacrolimus*	None	Dosed to achieve goal trough level of 2-5 ng/mL**	PO	Twice daily	N/A
Prednisone*	None	5 mg**	PO	Daily	

* Patients who have experienced allograft loss may discontinue tacrolimus and prednisone.
 ** Tacrolimus trough levels should be monitored each cycle while receiving Nivolumab/Ipilimumab in order to maintain 2-5 ng/ml.
 *** Patients may remain on higher-dose prednisone if already taking.
 IV=intravenous, PO=orally

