1.2 Secondary Objectives

1.2.1 To estimate the objective response rate (ORR), rate of allograft loss, and durations of progression-free survival (PFS) and overall survival (OS) in the study population.

1.2.2 To estimate the ORR and rate of allograft loss in patients who experience progressive disease (PD) after administration of nivolumab and 1) receive ipilimumab and nivolumab, or 2) decrease or discontinue immunosuppression.

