- Has been off study therapy for at least 90 days, but less than 1 year.

Patients who experience allograft loss should begin dialysis and may resume nivolumab monotherapy or nivolumab plus ipilimumab combination therapy, as appropriate.

Dose modifications of tacrolimus and prednisone should be done per standard of care.

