9. STATISTICAL CONSIDERATIONS

9.1 Study Design/Endpoints

9.1.1 Overview

A “success” rate (CR/PR/SD without allograft loss at 16 weeks) of 15% or lower (null hypothesis) would be considered insufficient for further study in this population, while a “success” rate of 40% or higher (alternative hypothesis) would be considered worthy of further investigation. This trial will be performed using a modified Simon’s two-stage minimax design (Simon, 1989). In the first stage, nine patients will be enrolled. To minimize risk to patients, accrual will be paused after the ninth patient is enrolled until a decision is made to continue the trial. If one or no patients experience CR/PR/SD without allograft loss at 16 weeks, the study will be temporarily closed to accrual for futility. Otherwise, 7 additional patients will be enrolled for a total of 16. The null hypothesis will be rejected if 5 or more patients experience CR/PR/SD without allograft loss. This design yields a type 1 error rate of 0.074 and power of 0.8 to distinguish between the null hypothesis and the alternative hypothesis.

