9.5 Analysis of Secondary Endpoints

Renal allograft rejection rate will be estimated as the proportion of subjects who experience markers of allograft rejection as defined in Section 7.2.

Allograft loss is defined as allograft rejection leading to complete, permanent, and irreversible loss-of-function of the renal allograft. All patients who receive at least one dose of nivolumab will be evaluable for allograft rejection.

Objective response rate (ORR) is defined as the proportion of subjects whose best overall response from baseline is either a CR or PR, based on RECIST 1.1 criteria. ORR will be estimated along with 95% exact CI. A minority of subjects treated with immunotherapy may derive clinical benefit and experience a delayed response, stable disease, or increased OS despite initial evidence of PD with nivolumab or combination treatment. Subjects who continue treatment beyond initial investigator-assessed, RECIST 1.1-defined progression will be considered to have investigator-assessed PD at the time of the initial progression event but may be later designated as delayed responses for purposes of determining ORR and counted as responses. The analysis of ORR will be performed on the response-evaluable population, defined as those subjects who have measurable disease at baseline, receive at least one dose of nivolumab, and undergo response assessments at ~8 and ~16 weeks. Patients who, in the opinion of the investigator, experience PD prior to 16 weeks will also be evaluable. Immune-related ORR based on immune-related response criteria (iRECIST) will also be summarized using the same method.

Among the patients who experience CR or PR, DOR is measured from the time criteria are met for CR/PR (whichever is first recorded) until the first date that recurrent disease or PD is documented. DOR will be summarized using the Kaplan-Meier method. All patients who experience CR/PR will be evaluable for DOR.

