Overall survival (OS) is the time from the first dose of nivolumab to the date of death from any cause. A subject who has not died will be censored at last known date alive. Progression-free survival (PFS) is defined as the time from the first dose of nivolumab to the date of the first documented tumor progression or death due to any cause, whichever occurs first. Subjects who did not progress or die will be censored on the date of their last evaluable tumor assessment. Kaplan-Meier curves will be used to summarize OS and PFS. OS and PFS analyses will be performed for all patients who receive at least one dose of nivolumab.

Because the number of patients who change over to nivolumab + ipilimumab or continue nivolumab with reduction in their immunosuppressive regimen after disease progression on nivolumab monotherapy will be small and unpredictable, data from these patients will be considered investigative and potentially hypothesis-generating.

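### Tumour responses first seen after graft loss and a change of regimen, without progression, enter the overall ORR unmarked; report an on-regimen ORR and DOR beside it

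*Combined protocol and SAP*

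**What the plan says.** **Treatment.** Two sections open a route after graft loss that does not depend on progression.

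- Section 6.3: "Patients who experience PD on single-agent nivolumab, or patients who have experienced allograft loss, may shift to a combination therapy".
- Section 7.2: "Patients who experience allograft loss should begin dialysis and may resume nivolumab monotherapy or nivolumab plus ipilimumab combination therapy, as appropriate".

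The text of 6.2 and 6.3 says that tacrolimus should be discontinued once the graft is lost.

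**Analysis.**

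- Objective 1.2.1 estimates ORR, graft loss, PFS and OS in the study population and names no regimen.
- Objective 1.2.2 deals with changes of treatment and is limited to PD: "To estimate the ORR and rate of allograft loss in patients who experience progressive disease (PD) after administration of nivolumab".
- The paragraph in 9.5 on patients who switch begins: "Because the number of patients who change over to nivolumab + ipilimumab or continue nivolumab with reduction in their immunosuppressive regimen after disease progression". It calls their data investigative and removes nobody from any endpoint.
- ORR in 9.5: "Objective response rate (ORR) is defined as the proportion of subjects whose best overall response from baseline is either a CR or PR". Section 12.1.4.3 closes the best-response window at progression or recurrence.
- PFS in 9.5 runs from the first nivolumab dose to progression or death in all dosed patients. It is censored only at the last evaluable tumour assessment.
- Section 9.5 also lets delayed responses after an initial PD count toward ORR.

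**The concern.** Section 2.4 gives as a knowledge gap what happens to tumour regression and graft loss when checkpoint inhibitors are combined with anti-rejection drugs. Section 6.2 treats added ipilimumab and reduced immunosuppression as separate options once the index regimen has failed, and objective 1.2.2 asks for response rates after them. A patient who loses the graft without PD can have the same changes of treatment but belongs to no post-switch group. With no progression event, the best-response window stays open and PFS time keeps accruing.

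A reader of the final report could then not tell how many responses arose on nivolumab with continued immunosuppression and how many only after it was withdrawn or ipilimumab was added. With at most 16 patients, one responder is enough to change how the ORR reads. If no rule is set beforehand, the way to present such a patient will be chosen with the result in view.

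**Working it through.** **1. The plan's own figure.** Section 9.1.1 tests a success rate "of 15% or lower (null hypothesis) would be considered insufficient for further study in this population" against one "of 40% or higher (alternative hypothesis) would be considered worthy of further investigation". "In the first stage, nine patients will be enrolled"; the trial stops with 1 success or fewer, and otherwise goes to 16 and rejects with 5 or more.

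P(reject | p) = Σ over x = 2 to 9 of Bin(x; 9, p) × P(Bin(7, p) ≥ 5 − x)

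- p = 0.15: 0.0743 (stated 0.074)
- p = 0.40: 0.815 (stated 0.8)

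Both reproduce. The present point does not alter them. Graft loss by week 16 is a failure under 9.1.1 and evaluable under 9.4, and graft loss after week 16, with any switch that follows it, comes after the primary assessment.

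**2. Following one patient through the rules.** Take a patient with stable disease who loses the graft, starts ipilimumab and then has a first PR.

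- Objective 1.2.2: not included, as there was no PD.
- Best overall response (12.1.4.3): window still open, so the PR is recorded.
- ORR (9.5): a responder, if in the response-evaluable set.
- DOR (9.5): starts at that PR.
- PFS (9.5): not censored at the switch.

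None of these rules makes graft loss, tacrolimus discontinuation or the first ipilimumab dose a cut-off or a subgroup.

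**3. Direction for ORR.** Let a be the patients whose first CR or PR precedes any regimen change, b those whose first CR or PR follows one, and n the evaluable patients. The reported ORR is (a + b)/n and the on-regimen ORR is a/n. The difference is b/n, which cannot be negative.

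**4. Size per patient.**

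- n = 16: 1/16 = 6.25 points. For example, 5/16 = 31.3% (exact 95% CI 11.0 to 58.7) becomes 4/16 = 25.0% (7.3 to 52.4).
- n = 9: 1/9 = 11.1 points.

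The ORR set in 9.5 needs measurable disease and assessments at about 8 and 16 weeks, or earlier PD. So n may be below 16, and some patients with early graft loss may drop out of it.

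**5. How many such patients.** The documents do not say. As assumptions only, let g be the share of patients who lose the graft without PD or prior response and continue treatment, and q the share of those who then respond. The expected shift is g × q, and the chance of at least one such responder among 16 is 1 − (1 − gq)^16.

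| g | q | Expected responders of 16 | ORR shift (points) | P(at least one) |
|---|---|---|---|---|
| 0.10 | 0.10 | 0.16 | 1 | 0.15 |
| 0.20 | 0.30 | 0.96 | 6 | 0.63 |
| 0.50 | 0.50 | 4.0 | 25 | 0.99 |

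The spread shows that the total cannot be forecast.

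**6. PFS.** As an illustration, assume exponential PFS with a median of 4 months, a switch at 2 months in 10% to 50% of patients, and a hazard ratio of 0.3 to 0.5 afterwards. The pooled median rises to between 4.1 and 5.3 months. That rise comes wholly from assuming that the switch helps; a hazard ratio above 1 would reverse it.

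**The case against.** **The plan never attributes these responses to the index regimen.** A reader might infer that it credits them to nivolumab plus tacrolimus plus prednisone. It does not: 1.2.1 speaks of the study population, and 2.4 describes the aim as nivolumab with or without ipilimumab. Following every dosed patient regardless of later treatment is a legitimate treatment-policy estimand. This stands, and it is why the all-follow-up figures should stay. But the plan does not declare that estimand, and it does not show how much of the ORR arose after a change.

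**Graft-loss switchers are not the only ones pooled.** Section 9.5 lets delayed responses after PD count toward ORR. Its switch paragraph can also be read so that the progression condition applies only to the reduced-immunosuppression group, which would make all ipilimumab switchers investigative. Both points stand. The cut-off must therefore cover changes after PD as well; the investigative label still takes no one out of ORR or PFS.

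**Table 1 does not give the frequency.** It is tempting to use its 5 graft losses among 8 kidney recipients with known outcome. None of the five is listed on tacrolimus: four were on prednisone or prednisolone alone and one on azathioprine with everolimus. The one kidney recipient listed on tacrolimus with prednisone kept the graft. Three of the five had tumour regression, so graft loss without progression is plausible, but its rate on this regimen is unknown.

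**An upward bias in every endpoint is not shown.** Suspected rejection leads to withheld nivolumab, a higher tacrolimus target and high-dose steroid (7.2), which could move PFS and DOR either way. This also stands.

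**Conclusion.** The gap is real and confined to secondary endpoints. Patients who lose the graft without PD may change regimen, and no definition in 9.5 or 12.1.4.3 marks that change. Their later first responses enter the 1.2.1 ORR unidentified, as may some delayed responses after PD.

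For ORR the direction is fixed: upward relative to the on-regimen count, by 6.25 points per responder if all 16 patients are evaluable and more if fewer are. That is not a comparison with what the same patients would have achieved had they stayed on the index regimen, which the trial cannot show. The total effect rests on a count that the documents do not give. No direction can be claimed for PFS or DOR, and the two-stage design keeps its stated properties.

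**What to change.** 1. In 9.5, keep ORR, DOR and PFS over all follow-up and label them as the study-population figures.
2. Beside them, report ORR and DOR using only assessments before the first regimen change. Define that change as the earliest of: first ipilimumab dose; discontinuation of tacrolimus after graft loss; reduction or discontinuation of immunosuppression after PD. State whether a response first seen before the change but confirmed after it counts.
3. Add patients who change regimen after graft loss without PD as a separate descriptive group under objective 1.2.2.
4. Treat any PFS analysis censored at the change as a sensitivity analysis only. Add the caveat that the censoring may be informative, because graft loss may reflect the same immune activation as tumour response.
5. Reconcile the passages that fix the cut-off date. On tacrolimus after graft loss, the text of 6.2 and 6.3 says it should be discontinued, the 6.3 table footnote says only that it may be, and 7.2 refers to standard of care. On continuing treatment, 6.7 lists signs of rejection among the reasons for ending therapy, while 6.3 and 7.2 allow treatment after graft loss.

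The cost is analysis wording, one more table column and possibly a lower on-regimen ORR. The dates should largely be on hand: 6.7 requires discontinuation dates on the case report form, 6.6 requires concurrent drugs to be recorded, and tacrolimus diaries are reviewed each cycle. Items 1 to 4 change no treatment rule.

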6.4 Treatment Beyond Progression

A minority of subjects treated with immunotherapy may derive clinical benefit (e.g., delayed response, stable disease, or increased OS) despite initial evidence of PD with nivolumab or combination treatment.

Patients may be permitted to continue treatment beyond initial RECIST 1.1-defined PD if, in the opinion of the investigator, they may benefit from doing so. In general, patients must be clinically stable with no change in performance status due to disease progression and there must be no indication for immediate alternative treatment.

6.5 Criteria to Resume Treatment

Some patients may continue to benefit from treatment, maintaining or improving their responses after disease progression, including those treated with steroids.

For non-autoimmune or non-inflammatory events patients may resume treatment with study drug(s) when the drug-related AE(s) resolve to \leq grade 1, or baseline value, with the following exceptions:

- An evaluation of endocrine, GI, hepatic, and pancreatic functions must be made prior to restarting to exclude any additional IMARs.
- Non-drug-related toxicity including hepatic or pulmonary toxicity, diarrhea, or colitis, must have resolved to baseline before treatment is resumed.

If the criteria to resume treatment are met, the patient should restart treatment no sooner than the next scheduled time point according to the protocol. However, if the treatment is delayed past the next scheduled time point per protocol the treatment should resume at the earliest convenient point that is within the six-week delay period.

A patient who is successfully treated for allograft rejection (*i.e.*, still has a functional kidney allograft) may restart study therapy after rescreening and consultation with the PI if the patient:

- Experienced an objective response or SD on study therapy,
- Experiences progressive or recurrent disease after having been off study therapy, and
- Has been off study therapy for at least 90 days but less than 1 year.

6.6 General Concomitant Medication and Supportive Care Guidelines

Because there is a potential for interaction of nivolumab or ipilimumab with other concomitantly administered drugs, the case report form must capture the concurrent use of all other drugs, over-the-counter medications, or alternative therapies. The study PI should be alerted if the patient is taking any agent known to affect or with the potential for drug interactions. The study team should check a frequently updated medical reference for a list of drugs to avoid or minimize the use of.

6.7 Duration of Therapy

In the absence of treatment delays due to AE(s), treatment may continue for 24 cycles or until one of the following criteria applies:

- Complete radiographic response;
- Signs of allograft rejection (see Section 7 for further information);
- Disease progression (see Section 7 for further information);
- Intercurrent illness that prevents further administration of treatment;
- AEs which require permanently going off study treatment (see Section 7 and specific algorithms in Appendix B);
- Any dosing interruption lasting >6 weeks, with the following exceptions:
 - Dosing interruptions >6 weeks that occur for non-drug-related reasons may be allowed if approved by the Investigator. Prior to re-initiating treatment in a subject

with a dosing interruption lasting >6 weeks, the study PI must be consulted. Tumor assessments should continue according to the protocol even if dosing is interrupted;

- Patient decides to withdraw from the study;
- General or specific changes in the patient's condition render the patient unacceptable for further treatment in the judgment of the Investigator;
- Patient non-compliance;
- Pregnancy:
 - All women of child-bearing potential should be instructed to contact the investigator immediately if they suspect they might be pregnant (*e.g.*, missed, or late, menstrual period) at any time during study participation;
 - The investigator must immediately notify CTEP in the event of a confirmed pregnancy in a patient participating in the study;
- Termination of the study by the study sponsor; or
- The drug manufacturer can no longer provide the study agents.

The reason(s) for protocol therapy discontinuation, the reason(s) for study removal, and the corresponding dates must be documented in the Case Report Form (CRF).

6.8 Duration of Follow Up

Follow-up visits should be scheduled as follows:

- All patients who receive study therapy will be monitored for SAEs and IMARs for 90 days after their last dose of nivolumab or ipilimumab. Patients will be followed via monthly phone calls.
- For patients except those who develop PD (*i.e.*, patients who complete 96 weeks of therapy or whose treatment is discontinued after a CR or drug toxicity): every 8 weeks (± 14 days) during the year immediately following cessation of therapy, then every 12 weeks (± 21 days) during the second year following cessation of therapy, then every 16 weeks (± 21 days) during the third year following cessation of therapy, then every 24 weeks (± 28 days) during the fourth year following cessation of therapy.
- Patients with documented PD will be contacted by telephone or other means (*e.g.*, email) every 12 weeks ± 14 days to assess for survival. Survival follow-up will continue until death or 5 years from the date of trial registration, whichever occurs first.

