12.1.4.3 Evaluation of Best Overall Response

The best overall response is the best response recorded from the start of the treatment until disease progression/recurrence (taking as reference for progressive disease the smallest measurements recorded since the treatment started). The patient's best response assignment will depend on the achievement of both measurement and confirmation criteria.

For Patients with Measurable Disease (*i.e.*, Target Disease)

Target Lesions	Non-Target Lesions	New Lesions	Overall Response	Best Overall Response when Confirmation is Required*
CR	CR	No	CR	≥4 wks. Confirmation**
CR	Non-CR/Non-PD	No	PR	≥4 wks. Confirmation**
CR	Not evaluated	No	PR	
PR	Non-CR/Non-PD/not evaluated	No	PR	≥4 wks. Confirmation**
SD	Non-CR/Non-PD/not evaluated	No	SD	
PD	Any	Yes or No	PD	no prior SD, PR or CR
Any	PD***	Yes or No	PD	
Any	Any	Yes	PD	

* See RECIST 1.1 manuscript for further details on what is evidence of a new lesion.

** Confirmatory scans should be obtained at least 4 weeks following initial documentation of response.

*** In exceptional circumstances, unequivocal progression in non-target lesions may be accepted as disease progression.

Note: Patients with a global deterioration of health status requiring discontinuation of treatment without objective evidence of disease progression at that time should be reported as “*symptomatic deterioration*.” Every effort should be made to document the objective progression even after discontinuation of treatment.

For Patients with Non-Measurable Disease (i.e., Non-Target Disease)

Non-Target Lesions	New Lesions	Overall Response
CR	No	CR
Non-CR/non-PD	No	Non-CR/non-PD*
Not all evaluated	No	not evaluated
Unequivocal PD	Yes or No	PD
Any	Yes	PD

* 'Non-CR/non-PD' is preferred over 'stable disease' for non-target disease since SD is increasingly used as an endpoint for assessment of efficacy in some trials so to assign this category when no lesions can be measured is not advised

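### Section 6.8 ties survival follow-up to why treatment stopped, so patients who stop without documented PD can be censored informatively in the OS analysis

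*Combined protocol and SAP*

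**What the plan says.** Section 6.8 has three follow-up bullets.

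- **All treated patients:** "All patients who receive study therapy will be monitored for SAEs and IMARs for 90 days after their last dose of nivolumab or ipilimumab". The same bullet adds "Patients will be followed via monthly phone calls".
- **Visits:** the lead-in is "For patients except those who develop PD". An *i.e.* clause then defines the group as "patients who complete 96 weeks of therapy or whose treatment is discontinued after a CR or drug toxicity". Visits run at widening intervals through the fourth year after therapy ends.
- **Survival contact:** "Patients with documented PD will be contacted by telephone or other means", every 12 weeks. The end point of death or 5 years from registration appears only in this bullet.

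Section 6.7 lists reasons for stopping that the *i.e.* clause does not name. They include "Intercurrent illness that prevents further administration of treatment", a change in the patient's condition, non-compliance and signs of allograft rejection. Section 12.1.4.3 recognises a further group: "Patients with a global deterioration of health status requiring discontinuation of treatment without objective evidence of disease progression at that time".

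Section 9.5 analyses OS in every patient given at least one nivolumab dose, with the rule "A subject who has not died will be censored at last known date alive". OS is named in secondary objective 1.2.1. The Follow-up column of the monotherapy calendar (section 11.1) refers back to 6.8, so it adds no other schedule.

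**The concern.** The Kaplan-Meier estimate assumes that a patient censored at a given time has the same outlook as those still followed. Here the length of planned contact depends on why treatment stopped, and that reason is often prognostic. A patient who stops because of illness or general decline is more likely than average to die in the following months. If contact lapses about 90 days after the last dose, deaths after that point may not be recorded. The curve then treats the patient as though the outlook matched that of the remaining cohort. Where such patients carry excess risk, the error runs towards better-looking survival. With at most 16 patients, each missed death shows in the curve, and contacts that were never made may not be recoverable later.

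**Working it through.** **1. The plan's own figure.** The documents give no sample size, event count or precision for OS. The only design calculation is in section 9.1.1. It is the sum over x = 2 to 9 of P(Bin(9, p) = x) × P(Bin(7, p) ≥ 5 − x). This gives 0.0743 at p = 0.15 (stated 0.074) and 0.815 at p = 0.40 (stated 0.8). It reproduces, and nothing in it depends on 6.8.

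**2. The passages side by side.**

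| Reason for stopping (6.7) | 6.8 after the 90-day calls, literal *i.e.* | 6.8 after the 90-day calls, broad lead-in |
|---|---|---|
| Documented PD | Every 12 weeks to death or 5 years from registration | Same |
| 96-week completion, CR, drug toxicity | Visits through year 4 after cessation | Same |
| Intercurrent illness, change in condition or non-compliance, no PD | Nothing scheduled | Visits through year 4 after cessation |
| Signs of allograft rejection, no PD | Visits only if classed as drug toxicity | Visits through year 4 after cessation |

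All four rows are in the OS set of section 9.5.

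**3. Length of follow-up on the broad reading.** Years from first dose = stopping week / 52.18 + 4, ignoring the short interval from registration to first dose.

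- Week 8: 0.15 + 4 = 4.15
- Week 16: 0.31 + 4 = 4.31
- Week 52: 1.00 + 4 = 5.00
- Week 96: 1.84 + 4 = 5.84

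A patient who stops without PD before about week 52 is followed for less than the 5 years given to PD patients. This includes CR and toxicity stoppers.

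**4. Possible size on the literal reading.** The documents give neither the number of such patients nor their survival, so every input here is an assumption. There are 16 treated patients. Those who do not stop this way have exponential survival with median 18 months. The other k patients stop for decline or illness at a uniform time in months 1 to 6, with median survival 4 months afterwards (varied from 2 to 6). Stopping is taken as the last dose, and nothing is learned about them more than 3 months later.

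True 12-month survival:

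- Other patients: 2^(−12/18) = 0.630.
- Stoppers: the average of 2^(−(12−u)/4) over u from 1 to 6 = (1/5)(4/ln 2)(2^(−1.5) − 2^(−2.75)) = 1.154 × (0.354 − 0.149) = 0.237.
- Cohort: [(16 − k) × 0.630 + k × 0.237] / 16.

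The Kaplan-Meier column adds the average excess found by simulating such 16-patient trials.

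| k of 16 | True 12-month OS | Excess | Kaplan-Meier with contact ending at 3 months |
|---|---|---|---|
| 2 | (8.82 + 0.474)/16 = 58.1% | +3.0 | 61.1% |
| 3 | (8.19 + 0.711)/16 = 55.6% | +4.5 | 60.1% |
| 4 | (7.56 + 0.948)/16 = 53.2% | +5.8 | 59.0% |

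With the median after stopping varied from 2 to 6 months, the excess is about 2.5 to 6 points for k = 2 to 4 and about 1.2 to 1.6 points for k = 1.

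**5. A second set of assumptions.** This used 400,000 simulated patients per scenario, exponential OS with median 12 or 24 months, and a death hazard after stopping of 1 to 8 times the base. With no excess hazard the bias is about zero (for example 50.1% against 50.1% with 4 of 16 and a 12-month median). At 2 to 8 times, 12-month OS is too high by 0.6 to 1.6 points with 1 of 16, about 1 to 3 with 2 of 16, and about 2 to 6 with 4 of 16.

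**The case against.** The strongest reply is the lead-in. Taken on its own it covers every patient without PD. A site reading it that way would see an ill or declining patient every 8 weeks in the first year, and the 12-month bias would not arise. This stands as a fair reading. It makes the defect a conflict inside one bullet, not a proven exclusion, and it leaves the unequal horizon in step 3.

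Section 12.1.4.3 asks sites to make every effort to document progression after symptomatic deterioration, and documented PD would move the patient into the 5-year contact. That is a real safeguard but a partial one, because it sets no schedule and does not cover intercurrent illness. Section 10.3.3 requires deaths on study to be reported, and under 9.5 a later death that the site happens to learn of still counts. Neither provides planned contact.

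Three stronger inferences are tempting, and the documents do not support them.

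- **That these patients' deaths vanish from OS.** The 90-day calls catch many. With a 3-month window, 1 − 2^(−3/4) = 41% of deaths fall inside it at a 4-month median, 65% at 2 months and 29% at 6 months.
- **That PFS is shown to be biased too.** PFS is censored at the last evaluable tumor assessment. No PFS effect has been computed, and survival calls would supply no scans.
- **That late OS rests mainly on progressed patients.** Completers are followed to about 5.84 years, longer than PD patients. On the broad reading, late censoring of early stoppers with a good outlook could even lower OS.

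The bias is also modest against sampling error: with 16 patients and survival near 56%, the binomial standard error is √(0.56 × 0.44/16), about 12 points. OS is secondary and descriptive, with no test attached.

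**Conclusion.** The point holds as an internal conflict in 6.8 with a foreseeable consequence for OS. On the literal text, patients who stop without documented PD for illness or decline have no planned contact after about 90 days but remain in the OS analysis, so their censoring can be informative and favourable. On the broad text, follow-up still differs by reason for stopping, and no direction of bias is claimed.

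Informative censoring is a risk that the wording creates; the documents do not establish that it will occur. The size rests wholly on the assumed number of such patients, their excess hazard and the absence of any later ascertainment: about 1 to 2 points at 12 months for 1 of 16, about 2.5 to 6 points for 2 to 4 of 16, and about zero without excess hazard. The 16-week primary endpoint, the stage decision and the stated error rates are unaffected. The change is worth making because it is cheap and OS is a named objective, but it does not threaten the trial's main conclusion.

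**What to change.** Make two edits to section 6.8.

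1. In the visit bullet, replace the *i.e.* list with: *patients who stop treatment for any reason other than documented PD*. This removes the conflict with the lead-in and settles how stops for rejection are handled.
2. Take the survival sentence out of the PD bullet and give it its own: *All patients who receive at least one dose of nivolumab will be contacted every 12 weeks ±14 days for survival until death or 5 years from registration, whatever the reason for stopping, unless consent for follow-up is withdrawn; a scheduled visit in the window counts as the contact.*

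The consent exception is needed because 6.7 lists patient withdrawal among the reasons for stopping. The cost is amendment wording and site time for a few extra calls or e-mails in at most 16 patients. No stated design figure changes.
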